APPENDIX 6 PHARMACODYNAMIC, PHARMACOGENOMIC, AND OTHER BIOMARKER RESEARCH

Subjects enrolled in this clinical study will have biologic samples collected for PD, PG, and other biomarker analysis. Optional subject consent must be obtained for banking of samples for future research. These samples may be used for discovery and validation to identify biomarkers that may be used for exploratory evaluation of response and/or safety-related outcomes as well as for use in diagnostic development.

The PG samples may be used to identify genetic factors that may influence a subject's exposure to the study treatment, as well as genetic factors that may have an effect on clinical response or potential adverse events related to study treatment, and to explore the role of genetic variability in response. Samples may be analyzed to determine a subject's genotypes or sequence for a number of genes or noncoding regulatory regions. The research may include the investigation of polymorphisms in genes that are likely to influence the PK or therapeutic response of the study treatment.

Collection of the pharmacodynamic, PG, and other biomarker samples will be bound by the sample principles and processes outlined in the main study protocol. Sample collection for pharmacodynamic, PG, and other biomarker analysis is required as per the study protocol unless the collection and use of the samples is prohibited by specific country laws.

Sample Collection and Handling

The samples will be collected according to the study flow chart. If, for operational or medical reasons, the genomic DNA blood sample cannot be obtained at the prespecified visit, the sample can be taken at any study center visit at the discretion of the investigator and site staff.

Security of the Samples, Use of the Samples, Retention of the Samples

Sample processing, for example DNA and/or RNA extraction, genotyping, sequencing, or other analysis will be performed by a laboratory under the direction of the Sponsor. Processing, analysis, and storage will be performed at a secure laboratory facility to protect the validity of the data and maintain subject privacy.

Samples will only be used for the purposes described in this protocol. Laboratories contracted to perform the analysis on behalf of the Sponsor will not retain rights to the samples beyond those necessary to perform the specified analysis and will not transfer or sell those samples. The Sponsor will not sell the samples to a third party.

Samples will be stored for up to 15 years after the completion of the study (defined as submission of the clinical study report to the appropriate regulatory agencies). At the end of the storage period, samples will be destroyed. Samples may be stored longer if a health authority (or medicinal product approval agency) has active questions about the study. In this special circumstance, the samples will be stored until the questions have been adequately addressed.

It is possible that future research and technological advances may identify genomic variants of interest, or allow alternative types of genomic analysis not foreseen at this time. Because it is not possible to prospectively define every avenue of future testing, all samples collected will be single or double coded (according to the ICH E15 guidelines) in order to maintain subject privacy.

Right to Withdraw

If, during the time the samples are stored, a subject would like to withdraw his/her consent for participation in this research, RAPT Therapeutics will destroy the samples. Information from any assays that have already been completed at the time of withdrawal of consent will continue to be used as necessary to protect the integrity of the research project.

Subject Privacy and Return of Data

No subject-identifying information (e.g., initials, date of birth, government identifying number) will be associated with the sample. All pharmacodynamic and other biomarker samples will be single coded. Genomic DNA samples used to explore the effects on PK, treatment response, and safety will be single coded. Genomic DNA samples that will be stored for long-term use (defined as 15 years after the completion of the study) will be double coded. Double coding involves removing the initial code (subject ID) and replacing with another code such that the subject can be re-identified by use of 2 code keys. The code keys are usually held by different parties. The key linking the sample ID to the subject number will be maintained separately from the sample. At this point, the samples will be double-coded, the first code being the subject number. Laboratory personnel performing genetic analysis will not have access to the “key.” Clinical data collected as part of the clinical trial will be cleaned of subject identifying information and linked by use of the sample ID “key.”

The Sponsor will take steps to ensure that data are protected accordingly, and confidentiality is maintained as far as possible. Data from subjects enrolled in this study may be analyzed worldwide, regardless of location of collection.

The Sponsor and its representatives and agents may share coded data with persons and organizations involved in the conduct or oversight of this research. These include:

- Clinical research organizations retained by the Sponsor
- Independent ethics committees or institutional review boards that have responsibility for this research study
- National regulatory authorities or equivalent government agencies

At the end of the analysis, results may be presented in a final report which can include part or all of the coded data, in listing or summary format. Other publication (e.g., in peer-reviewed scientific journals) or public presentation of the study results will only include summaries of the population in the study, and no identified individual results will be disclosed.

Given the research nature of the pharmacodynamic, PG, and other biomarker analysis, it will not be possible to return individual data to subjects. The results that may be generated are not currently anticipated to have clinical relevance to the subjects or their family members. Therefore, these results will not be disclosed to the subjects or their physicians.

If at any time, pharmacodynamic, PG, and/or other biomarker results are obtained that may have clinical relevance, IRB review and approval will be sought to determine the most appropriate manner of disclosure and to determine whether or not validation in a Clinical Laboratory Improvement Amendments (CLIA)-certified setting will be required. Sharing of research data with individual subjects should only occur when data have been validated by multiple studies and testing has been done in CLIA-approved laboratories.

APPENDIX 7 PROHIBITED MEDICATIONS AND THERAPIES

The following is a list of all medications, therapies (including procedures) that are prohibited while the subject is enrolled in this study. Subjects receiving any of these medications at study entry should discontinue the treatment or be switched to a different medication with similar pharmacology prior to starting study treatment. Subjects who receive any of these medications during the Treatment Phase must discontinue study treatment.

Medications that potentially prolong the QT interval

A list of medications known to cause QTc interval prolongation is provided in the table below and is also available at the following link:

<https://crediblemeds.org/pdftemp/pdf/CombinedList.pdf>. This list is not all-inclusive.

Compounds	Compound Half-Life	Possible Washout Period – Hours	Possible Washout Period - Days
Alfuzocin	~10 hours		7
Amantadine	17 +/- 4 hours (10–25)		4
Amiodarone (cordarone)	58 days (15–142) 36 days (active metabolite)		180
Amitriptyline*	> 24 hours, wide interpatient variability		
Arsenic trioxide	Not characterized		
Azithromycin	40 hours		
Bepridil	42 hours (26-64)		10
Chloral hydrate	Readily converted to Trichloroethanol (active metabolite T1/2 = 7–10 hours)	48	
Chloroquine	Prolonged (days to weeks)		
Chlorpromazine	30 +/- 7 hours		
Clarithromycin	Non-linear PK3-4 hr (250mg Q12) 5–7 hr (500 mg Q12)	36	
Cloroquine	6 to 60 days; mean 20 days		
Desipramine*	> 24 hours, wide interpatient variability		
Disopyramide	6.7 hr (4-10)	36	
Dofetilide	10 hours	48	
Dolesetron	8.1 hours		
Domperidone	7–8 hours	48	
Doxepin*	> 24 hours, wide interpatient variability		
Droperidol	2.2 hours	10	
Erythromycin	*Each salt form has different Half-Life*		
Felbamate	20–23 hours		5
Flecainide	20 hours (12–27)		5
Foscarnet	87.5 +/-41.8 hours *distribution and release from bone*		20

Compounds	Compound Half-Life	Possible Washout Period – Hours	Possible Washout Period - Days
Fosphenytoin	12–29 hours		6
Gatifloxacin	7–14 hours	48	
Gemifloxacin	7 hours	48	
Grepafloxacin	16 hours		3
Halofantrine	6–10 days (variable among individual)		45
Haloperidol	18 +/- 5 hours		5
Ibutilide	6 hours (2–12) *variable among subject*	36	
Imipramine*	> 24 hours, wide interpatient variability		
Indapamide	14 hours (biphasic elimination)		3
Isardipine	8 hours (multiple metabolites)	48	
Levofloxacin	6–8 hours	48	
Levomethadyl	Multiple compartment PK with active metabolite 2.6 days for LAAM, 2 day for nor-LAAM, 4 day for dinor-LAAM		20
Lithium	24 hours (10–50)		7
Mesoridazine	24–48 hours (animal study)		10
Methadone	15–30 hours		7
Moexipril/HCTZ	2–9 hour (include active metabolite) for moexipril; 5.6–14.8 hours for HCTZ	48	
Moxifloxacin	12 +/- 1.3 hours	72	
Naratriptan	6 hours	36	
Nicardipine	~ 2-hour post IV infusion	12	
Nortriptyline*	> 24 hours, wide interpatient variability		
Octreotide	1.7 hours	12	
Ofloxacin	5 to 7.5 hours		2
Ondansetron	4 hours (IV/IM); 3 hours (PO)		1 to 3
Pentamidine	6.4 +/- 1.3 hours	36	
Pimozide	55 hours		10
Procainamide	3–4 hours for PA and NAPA (active metabolite)	24	
Protriptyline*	> 24 hours, wide interpatient variability		
Quetiapine	6 hours	36	
Quinidine	6-8 hours in adult; 3–4 hours in children	36	
Quinine	4–5 hours		
Risperidone	3–20 hours (extensive to poor metabolizer)		4

Compounds	Compound Half-Life	Possible Washout Period – Hours	Possible Washout Period - Days
	9-hydroxyrisperidone (active metabolite) T1/2 = 21-30 hours (extensive to poor metabolizer)		
Salmeterol	5.5 hours (only one datum)	36	
Sotalol	12 hours	72	
Sparfloxacin	20 hours (16-30)		4
Sumatriptan	2.5 hours	12	
Tacrolimus	~34 hours in healthy; ~19 hours in Kidney transplant		7
Tamoxifen	5-7 days (biphasic)		30
Telithromycin	2-3 hours	24	
Thioridazine	20-40 hours (Phenothiazines)		7
Tizanidine	2.5 hours	12	
Vardenafil	4 to 5 hours		
Venlaflaxine	5 +/- 2 hours for parent comp. 11 +/- 2 hours for OVD (active metabolite)	60	
Ziprasidone	7 hours	36	
Zolmitriptan	2.8-3.7 hours (higher in female)	18	

*Weakly associated with Torsades de pointes and/or QT prolongation but that are unlikely to be a risk for Torsades de pointes when used in usual recommended dosages and in patients without other risk factors (e.g., concomitant QT prolonged drugs, bradycardia, electrolyte disturbances, congenital long QT syndrome, concomitant drugs that inhibit metabolism).

References: 1. Physician's Desk Reference 2002; 2. Facts and Comparison (update to June 2005);
3. The Pharmacological Basis of Therapeutics 9th Edition, 1999.

Known Strong Cytochrome P450 (CYP)3A4 Inhibitors or Inducers

Medication Type	Drug Names
CYP3A4 Inhibitors	
Strong inhibitors	boceprevir, clarithromycin, conivaptan, grapefruit-containing products, indinavir, lopinavir, mibefradil, nefazodone, nelfinavir, ritonavir, saquinavir, telaprevir, telithromycin
CYP3A4 Inducers	
Strong inducers	avasimibe, carbamazepine, phenytoin, rifampin, St. John's wort

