12. Known history of Hepatitis B (defined as Hepatitis B surface antigen reactive) or known active Hepatitis C virus (defined as detection of HCV RNA [qualitative]) infection.
13. Diagnosis of immunodeficiency or is receiving chronic systemic steroid therapy (at doses exceeding 10 mg daily of prednisone equivalent) or any other form of immunosuppressive therapy within 14 days prior to the first dose of study treatment.
Inhaled or topical steroids, and adrenal replacement doses of \leq 10 mg daily prednisone or equivalent are permitted in the absence of active autoimmune disease.
14. Prior allogeneic organ transplant.
15. Females who are pregnant, breastfeeding, or expect to become pregnant within the projected duration of the study, starting with the screening visit through 120 days after the final dose of study treatment. Males who plan to father children within the projected duration of the study, starting with the screening visit through 120 days after the final dose of study treatment.
16. Radiotherapy within 14 days prior to start of study treatment. Subjects must have recovered from all radiation-related toxicities, not require corticosteroids, and not have had radiation pneumonitis.
17. Subjects currently receiving treatment with any medications that have the potential to prolong the QT interval and that cannot be either discontinued or substituted with a different medication prior to starting study treatment. (See [Appendix 7](#))
18. Subjects currently receiving treatment with strong cytochrome P450 (CYP)3A4 inhibitors or inducers should discontinue such treatment or be switched to a different medication prior to starting study treatment. (See [Appendix 7](#))
19. Current participation in another study of an investigational agent or device.
20. Any illness, medical condition, organ system dysfunction, or social situation, including mental illness or substance abuse, deemed by the investigator to be likely to interfere with a subject's ability to sign informed consent, adversely affect the subject's ability to cooperate and participate in the study, or compromise the interpretation of study results.

9.1.3 *Replacement of Subjects*

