10.5.1 FLX475

For ongoing DLT assessment throughout both parts of the study, subjects will be monitored closely for treatment-emergent AEs (TEAEs) and laboratory abnormalities. [REDACTED]

[REDACTED]

[REDACTED]

If a subject experiences an AE, appropriate supportive care (e.g., antiemetics, antidiarrheals) should be instituted according to the nature of the event. In general, dose modifications of FLX475 are not permitted during the DLT Observation Period (Days 1–21 of Cycle 1). Subjects who experience a DLT during Cycle 1 should discontinue study treatment (unless it is determined to be in the subject's best interest to continue treatment by the investigator in consultation with the Sponsor's medical monitor).

For subjects receiving study treatment beyond Cycle 1, the following dose modification and discontinuation guidelines for FLX475 below should be considered. (Note that AEs known to be associated with ipilimumab but not previously observed with FLX475 monotherapy may not require modification of FLX475 dose.)

- For any clinically-significant organ-related Grade 4 TEAE (neurologic, pulmonary, cardiac, gastrointestinal, genitourinary, renal, hepatic, cutaneous) at least possibly related to FLX475, discontinue drug use permanently (unless it is determined by the investigator, in consultation with the Sponsor's medical monitor, to be in the subject's best interest to continue treatment, at a reduced dose).

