10.10.4 Prohibited Concomitant Therapies and Drugs

Medications or vaccinations specifically prohibited in the exclusion criteria are not allowed during this trial. If there is a clinical indication for any medication or vaccination specifically prohibited during the trial, discontinuation of study treatment or vaccination may be required. The investigator should discuss any questions regarding this with the Sponsor. The final decision on any supportive therapy or vaccination is at the discretion of the investigator or the subject's primary physician. However, the decision to allow the subject to continue to

receive study treatment requires the mutual agreement of the investigator, the Sponsor, and the subject.

Subjects are prohibited from receiving the following therapies during the Screening and Treatment Phase of this study:

- Antineoplastic systemic chemotherapy or biological therapy
- Immunotherapy not specified in this protocol
- Investigational agents other than ipilimumab or FLX475
- Radiation therapy

Note: Radiation therapy to a symptomatic solitary non-target lesion or to the brain may be allowed at the investigator's discretion.

- Live vaccines within 30 days prior to the first dose of study treatment and during participation in the study. Examples of live vaccines include, but are not limited to: measles, mumps, rubella, varicella/zoster, yellow fever, rabies, BCG, and typhoid vaccine. Seasonal influenza vaccines for injection are generally killed virus vaccines and are allowed; however, intranasal influenza vaccines (e.g., FluMist®) are live attenuated vaccines and are not allowed.
- Systemic glucocorticoids for any purpose other than to modulate symptoms from an AE that is suspected to have an immunologic etiology. The use of physiologic doses of corticosteroids may be approved after consultation with the Sponsor.

Note: Inhaled steroids are allowed for management of asthma or seasonal allergies. The use of prophylactic corticosteroids to prevent allergic reactions (e.g., IV contrast dye or transfusions) is permitted.

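### After a QT-prolonging or strong CYP3A4 medicine is started, Section 10.10.4 leaves room to continue study treatment by agreement, Appendix 7 requires stopping, and nothing says which prevails

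*Protocol*

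**What the plan says.** Exclusion criteria 17 and 18 (Protocol Section 9.1.2) cover the two classes, and both refer to Appendix 7. Criterion 17 concerns "Subjects currently receiving treatment with any medications that have the potential to prolong the QT interval" where these cannot be stopped or replaced. Criterion 18 says that subjects on strong CYP3A4 "inhibitors or inducers should discontinue such treatment or be switched to a different medication prior to starting study treatment".

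Section 10.10.4 carries the exclusion-criteria prohibitions into the treatment period. If a prohibited medicine becomes clinically indicated, "discontinuation of study treatment or vaccination may be required". A decision that the subject may continue to "receive study treatment requires the mutual agreement of the investigator, the Sponsor, and the subject".

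Appendix 7 lists the medicines in the two classes and states: "Subjects who receive any of these medications during the Treatment Phase must discontinue study treatment". Of its QT list it adds: "This list is not all-inclusive".

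Section 10.6 names FLX475 and ipilimumab as the study treatments. Section 9.1.4 provides for recording why either drug, or both, was stopped.

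**The concern.** Section 6.2 reports QTcF prolongation as the only dose-related effect of FLX475 seen so far. Section 6.1.3.2.2 describes one dose-limiting QTc event in the 75 mg and one in the 100 mg monotherapy cohort of FLX475-02, both in subjects with confounding factors. 100 mg is the dose used here. A second QT-prolonging drug is therefore a situation in which sites need a single instruction.

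The situation is foreseeable. Section 10.5.1 says that for an adverse event "appropriate supportive care (e.g., antiemetics, antidiarrheals) should be instituted according to the nature of the event", and ondansetron is on the Appendix 7 list. Section 10.10.3 permits antibiotics unless they are expected to interfere or interact with study treatment; azithromycin, levofloxacin and moxifloxacin are listed. Under one rule a subject given such a medicine comes off study treatment. Under the other, the same subject may stay on FLX475 by agreement, with no ECG condition attached to that agreement.

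**Working it through.** The conflict is one of text, so the first step sets the provisions side by side. The rest is counting.

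**1. Same medicines, different consequence**

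| | Section 10.10.4 | Appendix 7 |
|---|---|---|
| Scope | Medicines prohibited by the exclusion criteria, hence criteria 17 and 18 | QT-prolonging and strong CYP3A4 medicines |
| Stopping study treatment | Discretionary | Mandatory |
| Continuing | Contemplated, by three-way agreement | No exception |
| ECG condition on continuing | None | Not applicable |

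**2. Does other text settle it?** Section 10.10.4 later says that subjects who need the treatments named before it should come off the study. That sentence follows a bulleted list of chemotherapy or biologics, other immunotherapy, investigational agents, radiation, live vaccines and systemic glucocorticoids. Neither class is on that list. No sentence gives Appendix 7 precedence. SAP 7.3.2 counts an excluded concomitant treatment as an important deviation but says nothing about stopping.

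**3. When do the rules collide?** If the site stops study treatment, Appendix 7 is met, and so is 10.10.4, because its wording is permissive. If the parties agree to continue, 10.10.4 is met and Appendix 7 is breached. The collision is confined to this second case.

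**4. Scope of the list.** The QT table has 67 rows. Chloroquine appears under two spellings, which leaves 66. The CYP3A4 table has 13 inhibitors + 5 inducers = 18. Clarithromycin and telithromycin are on both lists. Distinct entries: 66 + 18 − 2 = 82. This measures how widely the rules diverge, not how often.

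**5. ECG cover for a subject who continues.** Table 6 footnote f schedules on-treatment triplicate ECGs on Cycle 1 Days 1 and 8 and on Day 1 of Cycles 2–6, then at end of treatment. The grid marks the whole Cycle 5+ column; it is the footnote that stops at Cycle 6.
- Last scheduled on-treatment ECG: Day 1 + 5 × 21 = Day 106.
- End of Cycle 35: 35 × 21 = Day 735.
- Day 1 visits with no scheduled ECG: 35 − 6 = 29 (Cycles 7–35), a span of 735 − 106 = 629 days.

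**6. Run-in.** Section 9.1.3 replaces a subject who receives under 80% of planned Cycle 1 doses for reasons other than DLT. For FLX475, 0.80 × 21 = 16.8, so 17 doses are needed. Counting the Day 1 ipilimumab dose, 0.80 × 22 = 17.6, so 18 in total, which is again 17 of FLX475. A subject stopped after 16 or fewer FLX475 doses is replaced; one who continues and reaches 17 stays among the six.

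**The case against.** The best defence is that there is no true contradiction. Section 10.10.4 is a general clause for a mixed group of medicines and vaccines, so permissive wording is natural there. Its agreement sentence can be read as a necessary condition on any continuation, not as a licence to override a stricter rule. The exclusion criteria send the reader to Appendix 7, which would then govern as the specific rule.

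That reading is available, but the protocol does not state it. Inclusion criterion 9(d) allows Sponsor-cleared exceptions for antiretrovirals with potential CYP interactions, so an absolute ban cannot simply be presumed to be the intent.

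Three further objections stand, in whole or in part:
- **Both rules cannot be followed.** A reader might infer this, but step 3 shows otherwise: always stopping satisfies both.
- **A subject who continues is unprotected.** A reader might infer this too. The documents do not support it: Section 10.5.1 has QTcF interruption, reduction and discontinuation rules with repeat ECG and electrolyte correction, and QTcF prolongation is both a DLT criterion (10.4) and an event of clinical interest (11.5.2). What remains is the period after Cycle 6, when no ECG is scheduled that would trigger those rules.
- **A single rule with a Sponsor exception keeps the discretion and softens Appendix 7.** This is fair. The gain is that the exception becomes explicit, documented and tied to monitoring. If the Sponsor wants no exceptions, stating that Appendix 7 governs would also remove the conflict.

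**Conclusion.** The inconsistency is real and should be corrected. It concerns the main known risk of FLX475 and covers every medicine in Appendix 7, but it operates only when the parties use the route to continue. Its frequency cannot be estimated, because the documents give no rate of use of listed medicines and none is assumed here.

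The substantive gap is that 29 of up to 35 Day 1 visits have no scheduled ECG, which matters for a subject kept on FLX475 with a listed medicine beyond Cycle 6. This rests on reading footnote f as limiting the grid.

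A reader might infer that the run-in decision or the reported results are compromised. The documents do not support that. The run-in effect needs a listed medicine in Cycle 1 of a six-subject cohort and a stop before dose 17. For deviations, a subject who continues is already flagged for an excluded medicine; only the additional label of meeting withdrawal criteria without being withdrawn depends on which rule governs. The SAP defines only the Full Analysis and Safety Analysis Sets, so that label excludes nobody, and efficacy is not summarised because the study stopped early. Both effects are minor.

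Read literally with Section 10.6, Appendix 7 stops both drugs. Section 8.2.2 foresees FLX475 alone after ipilimumab toxicity but not the reverse. Whether ipilimumab should continue alone is the Sponsor's design decision; the protocol need only state it.

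**What to change.** Put one identical rule in Section 10.10.4 and Appendix 7:

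- A listed QT-prolonging or strong CYP3A4 medicine that is started is stopped or substituted.
- If it cannot be, FLX475 is stopped, unless the Sponsor's medical monitor documents agreement to continue.
- If FLX475 continues, an ECG and electrolytes are checked before continuing and at each Day 1 visit while the medicine is taken, including after Cycle 6.
- The rule states whether the stop applies to FLX475 only or to both drugs.

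The cost is wording plus a few ECGs, only in subjects who continue. Day 1 ECGs through Cycle 6 are already scheduled, and electrolytes are already drawn pre-dose on study visit days (Table 6 footnote g). The ceiling, for a subject on a listed medicine from before Cycle 7 through Cycle 35, is 1 + 29 = 30 added ECG assessments. A short course would add one or two.
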